1.0 Objectives

1.1 Study Aims

The goal of this multi-center study is to determine how to tailor blood transfusion decisions to the quality of life (QOL) changes experienced by individual patients with myelodysplastic syndromes (MDS). We will assess this by piloting a peri-transfusion QOL assessment (PTQA) approach. The PTQA involves administering a QOL questionnaire (see Appendix A) to study participants before and after an upcoming transfusion appointment and comparing QOL scores.

Specific Aim 1

Assess the feasibility of PTQA. We will assess the feasibility of this new paradigm of decision support by determining the enrollment yield as a percentage of all patients approached. We will also assess feasibility by calculating the proportion of enrolled participants who complete both the pre- and post-transfusion the Quality of Life in Myelodysplasia Scale (QUALMS).

Specific Aim 2

Assess the potential usefulness of PTQA in improving clinical and utilization outcomes. We will use medical record review and match our participants to historical controls (matched for transfusion group; IPSS-R; pre-transfusion Hb; and institution) to assess our primary outcomes, which are:

1. The presence of second transfusion after PTQA (for transfusion-naive)
2. The number of red cell units used after PTQA (for transfusion-dependent)
3. The number of hospitalizations after PTQA (for both transfusion groups)
4. The number of clinic visits after PTQA (for both transfusion groups)

Specific Aim 3

Explore the potential impact of PTQA on patient-reported outcomes. At 8 weeks post-transfusion, we will send participants a follow-up questionnaire (see Appendix B) to assess the following secondary outcomes:

1. PTQA utilization
2. Decisional regret
3. Perception of care
4. Perceived stress

1.2 Study Hypothesis

We hypothesize that PTQA may help patients with MDS, primarily by decreasing transfusion use and its attendant iron overload. This includes patients who are starting transfusions (may hold off on additional transfusions if QOL does not improve) and the transfusion-dependent (may extend transfusion interval if QOL does not improve).

2.0 Background

2.1 Overview

The myelodysplastic syndromes (MDS) are bone marrow failure disorders that primarily affect the elderly. Up to 50,000 people are diagnosed with MDS each year in the United States^{1,2}, making them one of the most common hematologic malignancies. The disease can be clinically devastating, as patients who do not succumb to infections or bleeding often develop acute leukemia. Many also experience a severe decline in their QOL.^{3,4} The likelihood of increasing MDS incidence as the population ages has prompted the American Society of Hematology to include “finding an effective and personalized treatment” for MDS as one of its top research priority areas.⁵

While several potentially disease-modifying medications were approved in the mid-2000s, progress has been slower since,⁶ and red cell transfusions remain a mainstay of care. Unfortunately, chronic red cell transfusions have many disadvantages, including iron overload,⁷ decreased overall QOL among the transfusion-dependent,⁸ and increased stress on the national blood supply.⁹ Moreover, some patients experience improved QOL after transfusions, others do not.

While compromised QOL is often invoked to justify transfusions for patients with MDS, the question of whether or not QOL improves after transfusion remains unanswered due to several barriers.^{10,11} First, until recently, a rigorous tool to assess MDS-specific QOL did not exist. Second, research assessing when QOL concerns might outweigh physiologic ones has been limited by a lack of consensus regarding a minimum hemoglobin (Hb) that is safe for outpatients with MDS. Third, it has been difficult for researchers to systematically identify patients who would benefit from formal QOL assessment, such as those starting transfusions and the transfusion-dependent. Finally, while some patients likely experience improved QOL after transfusion, others do not, even at the same level of Hb. We thus propose that the key question is not whether transfusions improve QOL, **but how to tailor transfusion decisions to the QOL changes experienced by individual patients living with MDS.**

2.2 Relevant Preliminary Data

The QUALMS

From 2011 to 2015, we developed¹² and validated¹³ the Quality of Life in Myelodysplasia Scale (QUALMS), a rigorous QOL assessment tool for patients with MDS (see Appendix A and Protocols 10-461 and 13-346). With excellent internal consistency, known groups validity and responsiveness, the QUALMS has rapidly been incorporated into several MDS registries in the U.S., Canada, and Europe. In this current protocol, we will use the QUALMS to implement a new paradigm of transfusion support for patients with MDS that integrates peri-transfusion QOL assessment (PTQA). The PTQA will involve administering the QUALMS before and after red cell transfusions to determine whether the patient experiences any changes in QOL. Pre- and post-transfusion surveys will be scored, compared, and compiled in a report for patients and providers. These PTQA results will help guide future therapy decisions: if QOL post-transfusion is worse for a particular patient, a decrease in transfusions will be encouraged.

PROTOCOL TITLE: A New Paradigm of Transfusion Decision Support for Patients with MDS: Using Peri-Transfusion Quality of Life Assessments (PTQAs)

Minimum Safe Hb Level

At present, the optimal transfusion strategy for outpatients with MDS remains unknown. While high-quality studies of liberal versus restrictive transfusion practices have been conducted for other patient populations, there are sparse data on the minimum Hb level at which it is safe to forgo transfusions for non-hospitalized patients with MDS.

TRICC, the first of several inpatient studies, demonstrated that a restrictive transfusion strategy (Hb threshold of 7.0 g/dL) was effective and possibly superior to a liberal transfusion strategy (Hb threshold of 10.0 g/dL) in decreasing the 30-day mortality of **critically ill patients** in the intensive care unit, with the possible exception of patients experiencing acute coronary syndromes.¹⁴ A second inpatient study, FOCUS, examined the effects of a restrictive transfusion strategy (triggered by symptoms of anemia or at physician discretion for a Hb of <8 g/dL) versus a liberal strategy (triggered by Hb threshold of 10 g/dL) on **hip surgery patients with high cardiac risk**. This study found that a liberal transfusion strategy did not reduce rates of death or disability with respect to 60-day follow-up.¹⁵ TRACS, an additional inpatient study, found that a restrictive perioperative transfusion strategy (hematocrit less than 24%) was as safe as a liberal strategy (hematocrit less than 30%) in patients undergoing **elective cardiac surgery**.¹⁶

The above studies focused almost exclusively on inpatients without bone marrow failure or MDS. In contrast, few studies have assessed transfusion strategies in patients with MDS. A 2015 Cochrane review regarding the impact of transfusion practices on patients with bone marrow failure syndromes such as MDS found only one completed randomized trial (13 subjects in the Netherlands, published as abstract only).¹¹ The quality of the evidence was “very low” across different outcomes according to GRADE methodology, and the study mentioned did not report effects of transfusion on QOL. The reviewers did also identify two ongoing trials specific to MDS (one in Canada [NCT02099669] and the other in the UK [ISRCTN26088319]), each with an accrual goal of less than 40 patients, and both testing different Hb thresholds. The authors firmly concluded that “further randomized trials with robust methodology are required to develop the optimal transfusion strategy for MDS patients.”

For patients without MDS, the literature suggests a consensus on hemoglobin thresholds for restrictive versus liberal transfusion strategies. A 2016 Cochrane review of thresholds to guide transfusions found that among 31 trials—mostly of inpatients—about half used a restrictive transfusion threshold of 7 g/dL and the other half used a threshold between 8-9 g/dL. The studies found no evidence that a restrictive transfusion strategy impacted 30-day mortality or morbidity compared with a liberal transfusion strategy, although there was more uncertainty concerning patients with hematologic malignancies and bone marrow failure.^{17,18}

In view of the sparsity of data, in March 2018 we conducted a qualitative study with MDS experts (see Protocol 18-064) to determine the lowest Hb level at which, given no end-organ effects of anemia, outpatients with MDS can safely forgo transfusions. We utilized the modified Delphi technique, incorporating elements from the Rand/UCLA Appropriateness method (RAM).^{19,20} This is a formal method of working with experts to achieve consensus, involving three rounds of assessments and anonymous feedback from experts to each other between rounds.

PROTOCOL TITLE: A New Paradigm of Transfusion Decision Support for Patients with MDS: Using Peri-Transfusion Quality of Life Assessments (PTQAs)

Per Protocol 18-604, we convened an expert panel of 13 MDS physicians (12 MDS experts; 1 blood bank physician) at the national AAMDSIF Symposium to determine the minimum safe Hb level. All panel participants received a literature review and questionnaire via email prior to the in-person panel. This questionnaire comprised round one of the modified Delphi. Among several critical questions (see Protocol 18-604), we asked: *“Please mark the lowest hemoglobin at which you think it would be safe to forgo transfusions for patients with MDS given no evidence of end-organ damage.”* Once we received participants’ responses, we tabulated them and provided a summary of the results to the experts at our in-person panel. We allowed time for open discussion of each question. Following this discussion, we asked participants to fill out a round two questionnaire, the results of which were compiled and disseminated via email. We then asked the expert panel to fill out a third round of questions via email. While we were unable to reach a consensus threshold of 75% after three rounds, **we did have 100% consensus that the minimum safe Hb level should be no less than 7.5 g/dL.**

Accordingly, we will use this threshold to identify eligible patients for our study, meaning patients with an Hb level less than 7.5 g/dL will be ineligible for participation.

Epic Workbench Report

To systematically identify patients who would benefit from PTQA, a member of our study team, [name] (Medical Director for Clinical Information Systems at DFCI), is currently working with DFCI’s Epic team to create a Workbench report. This report will identify patients with MDS that are facing transfusion decisions. Epic is an EHR that covers 190 million patients in the U.S., including at the three centers participating in this project. Since May 2015, Epic has been the enterprise EHR for DFCI/BWH. It was previously adopted by Yale Cancer Center (YCC; 2013) and Wake Forest Baptist (WFB; 2012), the other two pilot sites.

Recent work has harnessed Epic data capture for cancer staging²¹ and surgical metrics;²² [name] is similarly working with the Partners Epic reporting group to create Workbench Reports to use in this current protocol. To ensure high quality care for patients who receive blood products, the Epic team at DFCI/BWH created sophisticated order sets to facilitate transfusion ordering. Using our Workbench Report, data elements from these sets will be mined to identify patients with MDS who might benefit from PTQA.

Our Workbench Reports will identify (1) patients with MDS who have not yet been transfused, but have Hb levels approaching 8.5 g/dL during our study’s enrollment period (to identify those heading toward first transfusion); and (2) patients with more than one transfusion during an 8 week period (to identify the transfusion-dependent; we will use the IWG criteria,²³ but not restrict to Hb \leq 9.0]). We are working with the Epic teams at YCC and WFB to ensure that they are able to use an identical report at their institutions to systematically identify patients for PTQA at these sites.

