3.2 Inclusion/Exclusion Criteria

Inclusion criteria:

1. Age \geq 18 years of age
2. Patients with MDS, including t-MDS and MDS/MPN
3. Transfusion-naive group: approaching Hb of 8.5 g/dL during enrollment period
 - a. Ideally never-transfused (have never received red cell transfusion)
 - b. If not never-transfused, participants are also eligible for inclusion in this group if they have not been transfused with red cells within last 8 weeks
4. Transfusion-dependent group: Patients with \geq 1 transfusion scheduled during 8-week period prior to enrollment
5. Ability to read and understand English

Exclusion criteria:

1. Age $<$ 18 years
2. Cr $>$ 2
3. Known CHF
4. Unstable Angina
5. Hb level below 7.5 g/dL
6. No plans for potential future outpatient transfusion.

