9.2 Study Procedures

Please see study schema (Appendix C) for study flow.

Pre-Transfusion

- Once identified by Epic scheduling report, provider suggestion, or study-specific Epic Workbench report, eligible patients will be approached for consent discussion at an appointment with their provider.
 - Patients with Hb approaching 8.5 g/dL will be approached at an appointment prior to an upcoming transfusion.
 - Patients that are transfusion-dependent will be approached at an upcoming appointment with their provider or during a transfusion appointment.
- During this initial encounter, consenting participants will be given a study packet containing a paper copy of the QUALMS. Study participants will be instructed to fill out the survey on the day before their upcoming pRBC transfusion.

**PROTOCOL TITLE: A New Paradigm of Transfusion Decision Support for Patients with MDS:
Using Peri-Transfusion Quality of Life Assessments (PTQAs)**

3. Study participants will indicate whether they would like to receive PTQA reports in person, via mail, or via email.
4. Site RAs will call study participants using script (see Appendix D) on the day prior to an upcoming transfusion to remind them to complete the QUALMS and bring it with them to their transfusion.
5. Note: Index transfusion is defined as any upcoming transfusion appointment for which the participant has completed both the pre- and post-transfusion QUALMS questionnaires.
 - If a participant does not complete the pre-transfusion questionnaire for any reason (i.e., participant forgot to complete at home or forgot to bring in), then the RA may ask the participant to complete the questionnaire at home prior to a subsequent transfusion appointment. This subsequent transfusion will become the index transfusion.
 - If a participant does not complete the pre-transfusion QUALMS at home prior to the appointment and there are extenuating circumstances (i.e., participant does not regularly receive transfusions at the site), then the RA may ask the participant to complete the questionnaire in clinic before his/her planned index transfusion.

Post-Transfusion

6. On the day of transfusion, the site RA will collect the completed pre-transfusion QUALMS survey. Study participants will then receive a second paper copy of the QUALMS, along with a stamped envelope addressed to the appropriate site.

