11.2 Power Analysis

Transfusion-naive patients: With a type I error of 5% and a sample size of 60 transfusion-naive patients total (30 PTQA versus 30 historical controls), we will have 85% power to detect changes in the proportion of transfusion-naive patients receiving second transfusion from 100% to 70%.

Transfusion-dependent patients: With a type I error rate of 5% and a sample size of 60 transfusion-dependent patients total (30 PTQA versus 30 historical controls), we will have 83% power to detect a decrease in mean number of units received from 8.0 to 6.5 if the standard deviation is 2.0 units.

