22.0 Recruitment Methods

22.1 Recruitment Procedure

Once the RA has identified potential study participants and confirmed eligibility with the patients' provider, potential study participants will be informed of the study at the appointment prior to their first/next transfusion.

- Patients that are nearing first transfusion will be approached at the appointment prior to their first transfusion.
- Patients that are transfusion-dependent will be approached at an upcoming appointment or transfusion.

Study consent will take place during these visits. Potential participants will be given the opportunity to ask questions, opt out of consideration, and take a consent form home to discuss further with their family and/or other clinicians. We will be clear that enrollment does not mean patients are required to forgo future transfusion if the resulting PTQA report indicates an unimproved or worsened QOL post-transfusion.

Once consented, all DF/HCC study participants will be registered in the DFCI OnCore Clinical Trial Management System by the RA as required by DF/HCC SOP REGIST-101.

- 22.2** The source population for this study is patients with MDS that are presenting to clinic for treatment with blood transfusion.
- 22.3** Eligible subjects will be identified using our study-specific Epic Workbench Report (as described above).

22.4 NA

22.5 NA

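### The transfusion-dependent group is defined by two different transfusion counts, and the protocol does not say which one selects its matched historical controls

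*Protocol*

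**What the plan says.** Two passages of the protocol define the transfusion-dependent group.

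- Section 2.2 (Epic Workbench Report) flags "patients with more than one transfusion during an 8 week period". It adds that, "to identify the transfusion-dependent; we will use the IWG criteria", without that rule's haemoglobin limit.
- Section 3.2, inclusion criterion 4, requires one or more, worded as "transfusion scheduled during 8-week period prior to enrollment".

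The neighbouring naive group in Section 3.2 takes previously transfused patients only "if they have not been transfused with red cells within last 8 weeks".

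On the route into the study, Section 3.1 allows clinic schedule reports as well as the Workbench report. Section 9.2 names three routes: "Once identified by Epic scheduling report, provider suggestion, or study-specific Epic Workbench report". Item 22.3 names the Workbench report alone.

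Specific Aim 2, Section 8.1, Section 11.1 and Appendix F match participants 1:1 to 2015–2017 controls on transfusion group, IPSS-R, pre-transfusion haemoglobin and institution. The two transfusion groups are analysed separately. For the dependent group, the primary outcome is red cell units in the 8 weeks after the index transfusion. Section 11.2 claims 83% power with 30 per arm for "a decrease in mean number of units received from 8.0 to 6.5", at a standard deviation of 2.0. Section 9.4 collects the number or frequency of transfusions before the index transfusion for dependent patients, but this is not a matching factor.

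**The concern.** The two definitions differ in three respects: the count (at least two against at least one), the basis (Section 3.2 counts scheduled transfusions, Section 2.2 does not say), and the anchor (Section 3.2 counts back from enrollment, Section 2.2 uses any 8-week period). Historical controls were never enrolled, so the Section 3.2 window cannot be applied to them as written.

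This matters because prior transfusion intensity probably predicts the outcome, which is itself a count of units. A group label that can mean either rule does not ensure that the two arms hold the same mix of lightly and regularly transfused patients, and none of the other three matching factors measures transfusion frequency directly. An imbalance in that mix would be read as an effect of PTQA, or would hide one. The planning mean and standard deviation also describe a population that the protocol does not identify.

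**Working it through.** **1. The plan's own figure.** Inputs from Section 11.2: 30 per arm, difference 8.0 − 6.5 = 1.5, SD 2.0, type I error 5%. Two-sided normal approximation: standard error = 2.0 × √(2/30) = 0.516; 1.5 / 0.516 = 2.905; 2.905 − 1.960 = 0.945; power = Φ(0.945) = 0.828. A two-sided t-test gives 0.815. The stated 83% reproduces, so the arithmetic is sound. The open question is which population the inputs describe.

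**2. The definitions side by side**, by number of red cell transfusions received in the last 8 weeks:

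| Received | Section 2.2 count | Section 3.2 count |
|---|---|---|
| None | not dependent | not dependent, unless one was scheduled and not given |
| Exactly one | not dependent, and barred from the naive group | dependent |
| Two or more | dependent | dependent |

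The rules part at exactly one. Because Section 3.2 counts scheduled visits, a patient whose only scheduled transfusion did not take place could meet the dependent criterion and also the naive group's 8-week condition.

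**3. Size of a possible bias.** Let p_P and p_C be the shares of lightly transfused patients among participants and controls, and D the difference in 8-week unit use between regularly and lightly transfused patients. With no PTQA effect at all,

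shift in mean = (p_P − p_C) × D.

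The protocol gives neither the shares nor D. Assume that regular patients use 8 units and light ones 2, so D = 6:

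- equal shares: 0 × 6 = 0;
- 10-point difference: 0.10 × 6 = 0.6 units, or 0.6 / 1.5 = 40% of the planned difference;
- 20-point difference: 0.20 × 6 = 1.2 units, or 1.2 / 1.5 = 80%.

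With light patients at 1 to 3 units (D = 7 to 5), the shifts are 0.5 to 0.7 at 10 points and 1.0 to 1.4 at 20 points. The sign follows the imbalance: more light patients among participants imitates a PTQA effect, and more among controls conceals one.

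**4. Power if both arms use the looser count.** Equal shares remove the bias but widen the distribution. Assume that 8.0 (SD 2.0) describes the regular patients, that light ones use 2 (SD 1), and that the relative reduction is the same, 1.5 / 8.0 = 18.75%. For a share f of light patients:

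mean = (1 − f) × 8 + f × 2; variance = (1 − f) × 4 + f × 1 + f(1 − f) × 36.

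- f = 10%: mean 7.4, variance 6.94, SD 2.63, difference 1.39; t-test power 52%.
- f = 20%: mean 6.8, variance 9.16, SD 3.03, difference 1.28; t-test power 36%.

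With light patients at 1 to 3 units, power is 45% to 59% at f = 10% and 29% to 45% at f = 20%. If the full 1.5-unit difference is kept and light patients use 2 units, power is 58% and 47%.

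**The case against.** The strongest reply is that Section 3.2 governs eligibility. The Workbench report stands under preliminary data, is described as still being built, and only produces a list that Section 3.1 sends on for eligibility checking. A screen narrower than the criterion does not redefine the group, and on the ordinary reading the Section 3.2 rule would apply to both arms. This stands as a reading of eligibility. It does not settle control selection, since the rule is anchored at an enrollment that controls never had, and it leaves the enrolled mix dependent on the route by which patients are found.

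A second reply concerns the index transfusion. Sections 9.2 and 11.1 require an upcoming transfusion that is actually received, so a participant with one received earlier has had at least two when follow-up begins. That narrows the gap between the rules. It does not close it where the interval is longer than 8 weeks or the scheduled visit did not happen.

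Third, Section 9.4 already collects prior frequency for participants, so the mix can be described. This stands, and it makes the remedy cheap, but a comparison with controls needs the same variable for them.

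The documents do not support three stronger readings that a reader might infer:

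- *That controls are found by the Workbench rule, so that bias is built in.* No section says so. Section 2.2 gives the report's purpose as finding patients for PTQA.
- *That the mean is off by 1.2 units.* That needs, for example, 20% light patients among participants and none among controls.
- *That a mean of 8.0 units shows the stricter count was intended.* Nothing ties it to either count. At an assumed 2 units per visit, two transfusions are 4 units, and 8.0 needs four.

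**Conclusion.** The contradiction is explicit and concerns the group that defines a primary outcome, its power statement and a matching factor. What follows is a risk of bias, of size (difference in share) × (difference in unit use). On the assumed 6-unit contrast this is 0.6 units at 10 points and 1.2 at 20, against a target of 1.5, and zero if the shares agree. The shares and unit use are assumptions, because the protocol gives neither. That the two arms will in fact be selected by different rules is not stated anywhere and should not be asserted.

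The 83% power is correctly computed. Whether it applies depends on which definition the mean of 8.0 and SD of 2.0 describe. The figures of 52% and 36% show how sensitive it is under one assumed mixture and are not corrected values.

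**What to change.** - Reconcile Sections 2.2 and 3.2 to one definition that states the count, the 8-week window, and whether transfusions are scheduled or received. Which count to use is for the investigators to decide.
- Apply it identically to both arms: participants anchored at enrollment or at the index transfusion, controls at their own index transfusion.
- Add the number of transfusions in the 8 weeks before index as a matching factor or an adjustment covariate. Section 9.4 collects prior number or frequency for participants without naming a window, so the window must be fixed and the variable abstracted for controls as well.
- State in Section 11.2 which definition the 8.0-unit mean and SD of 2.0 describe, and restate the power if they do not fit the definition chosen.

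The cost is a protocol amendment, one extra chart variable for controls, and slightly harder matching if the variable becomes a fifth matching factor. If the stricter count is chosen, patients with exactly one transfusion in 8 weeks would fit neither group, and the amendment must say how they are handled.
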